7.4. Dose Adjustment Criteria

7.4.1. Dose Adjustment for Tazemetostat

Tazemetostat dose reductions and interruptions will be allowed; however, an interruption in the administration of tazemetostat for more than 14 days must be discussed with the Medical Monitor before treatment can be resumed.

Toxicity will be managed by concomitant medication (as appropriate), treatment interruption, dose reduction, and treatment discontinuation, or a combination of these. During treatment with tazemetostat, dose interruption and reduction for subjects who experience tazemetostat-**related** toxicity will be in accordance with the Dose Modifications instructions in Table 1.

For subjects who require dose interruption due to tazemetostat-related toxicity, the treatment may restart once the toxicity has been resolved to Grade ≤ 1 or baseline, unless otherwise noted, according to the Dose Modifications instructions in Table 1. No tazemetostat dose re-escalation is permitted.

For continuation of treatment for Cycle 2 and beyond, subjects must meet the following retreatment criteria:

- Platelet count must be $> 50 \times 10^9/L$
- Absolute neutrophil count (ANC) must be $\geq 0.75 \times 10^9 / L$, and
- Any Grade 3 or higher toxicity must have resolved to ≤Grade 1 or baseline, unless otherwise noted

Table 1: Dose Modifications for Tazemetostat Treatment-Related Toxicities

Tazemetostat-Related Toxicity ^a	During Therapy	Approximate Dose Adjustmentb			
	Grade 1				
All occurrences	All occurrences Continue tazemetostat				
	Grade 2 ^{c,d}				
1st occurrence		Maintain dose level			
2 nd occurrence (same or new toxicity)	Interrupt tazemetostat until	Restart at 600 mg BID			
3 rd occurrence (same or new toxicity)	resolved to Grade ≤ 1 or baseline ^b	Restart at 400 mg BID			
4 th occurrence (same or new toxicity)		Discuss with Medical Monitor			
Grade 3 ^c (Not Including Neutropenia and Thrombocytopenia)					
1 st occurrence		Restart at 600 mg BID			

Tazemetostat-Related Toxicity ^a	During Therapy	Approximate Dose Adjustmentb						
2 nd occurrence (same or new toxicity)	$\begin{array}{c} \text{Interrupt tazemetostat until} \\ \text{resolved to Grade} \leq 1 \text{ or baseline}^b \end{array}$	Restart at 400 mg BID						
3rd occurrence (same or new toxicity)	Discontinue tazemetostat	Not applicable						
Grad	Grade 3 Neutropenia (ANC: < 1.0 – 0.5 × 10 ⁹ /L) ^e							
ANC $\ge 0.75 \times 10^9 / L$	Continue tazemetostat	Maintain dose level						

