$ANC < 0.75 \times 10^9/L$ 1 st occurrence	Interrupt tazemetostat until	Restart at 600 mg BID						
2 nd occurrence	resolved to ANC $\geq 0.75 \times 10^9/L$	Restart at 400 mg BID						
3 rd occurrence	Discontinue tazemetostat	Not applicable						
	Grade 3 Thrombocytopenia ^f							
1st occurrence	Interrupt tazemetostat until	Restart at 600 mg BID						
2nd occurrence	resolved to Grade ≤ 2 or baseline ^b	Restart at 400 mg BID						
3rd occurrence	Discontinue tazemetostat	Not applicable						
Grade 4								
Any occurrence	Interrupt tazemetostat until resolved to Grade 2 or less	Discuss with Medical Monitor						

ANC = absolute neutrophil count, ASCO = American Society of Clinical Oncology; BID = twice daily

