9.2.5. Prohibited Concomitant Therapies and Drugs

Subjects must not receive other antitumor therapies while on study. Prohibited antitumor medications during this study are any other investigational or unapproved drugs, and other anticancer therapies unless otherwise stated. If a subject receives any prohibited antitumor medications, this will be judged as evidence of disease progression, and study drug will be discontinued. In this case, the subject should complete all off-treatment assessments and be followed for survival in the Survival Follow-up period.

Known strong CYP3A inhibitors and strong or moderate CYP3A inducers (including St. John's wort) are prohibited within 14 days prior to the first dose of study drug (tazemetostat) and for the duration of the study. Coadministration of tazemetostat with a strong or moderate CYP3A inhibitor increases tazemetostat plasma concentrations, which may increase the frequency or severity of adverse reactions.

Coadministration of tazemetostat with a strong or moderate CYP3A inducer may decrease tazemetostat plasma concentrations, which may decrease the efficacy of tazemetostat. Because there is a potential for interaction of tazemetostat with other concomitantly administered drugs through the cytochrome P450 system, all over-the-counter medications, and alternative therapies, in addition to prescribed medications, must be recorded in the eCRF. The Investigator should be alerted if the subject is taking any agent known to affect or with the potential to affect selected CYP450 isoenzymes.

Medications that are strong CYP3A inhibitors and strong or moderate CYP3A inducers include, but are not limited to, those listed in Table 4 (refer to product information and the source websites in Table 4 for the most up-to-date information).

Table 4: Examples of Strong and Moderate Clinical CYP3A Inhibitors and Inducers and Clinical CYP3A Sensitive Substrates for P450-Mediated Metabolisms

Strong Inhibitors	Moderate Inhibitors	Strong Inducers	Moderate Inducers	Sensitive Substrates
boceprevir	aprepitant	apalutamide	bosentan	alfentanil
clarithromycin ^a	ciprofloxacin	carbamazepine	efavirenz	avanafil
cobicistata	conivaptan ^d	enzalutamide ^f	etravirine	budesonide
danoprevir and	crizotinib	mitotane	phenobarbital	buspirone
ritonavir ^b	cyclosporine	phenytoin	primidone	conivaptan
elvitegravir and	diltiazeme	rifampin		darifenacin
ritonavir ^b	dronedaronea	St. John's wortg		darunavir ^h
grapefruit juice ^c	erythromycin			dasatinib

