9.2.6. Concomitant Medications to be used with Caution

The following medications are to be used with caution:

- CYP3A sensitive substrates
- Moderate CYP3A inhibitors. If coadministration with a moderate CYP3A inhibitor cannot be avoided, reduce the dose of tazemetostat as shown in Table 5. After discontinuation of the moderate CYP3A inhibitor for 3 elimination half-lives, resume the tazemetostat dose that was being taken prior to initiating the inhibitor.

Table 5: Tazemetostat Dose Reduction for Coadministration with Moderate CYP3A Inhibitors

Current Dosage	Adjusted Dosage
800 mg twice daily	400 mg twice daily
600 mg twice daily	400 mg for first dose and 200 mg for second dose
400 mg twice daily	200 mg twice daily

Examples of CYP3A sensitive substrates and moderate CYP3A inhibitors include, but are not limited to, those listed in Table 4. This list of medications is not exhaustive; refer to product information and the source websites in Table 4 for the most up-to-date information.

Refer to product information for rituximab for guidance regarding concomitant medications use and cautions related to interaction with other medications.

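### Read literally, Protocol 9.2.6 restores a tazemetostat dose level that Table 1 removed for toxicity during a moderate CYP3A inhibitor course, contrary to the re-escalation ban in 7.4.1 (minor)

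*Protocol*

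**What the plan says.** **Toxicity rule (Protocol 7.4.1 and Table 1).** "For subjects who require dose interruption due to tazemetostat-related toxicity", treatment restarts according to Table 1. The first step down is "Restart at 600 mg BID" (first Grade 3 or second Grade 2 event). The second is 400 mg BID (second Grade 3 or third Grade 2 event). A third Grade 3 event means discontinuation. A fourth Grade 2 event and any Grade 4 event carry the instruction "Discuss with Medical Monitor". The paragraph on restarting closes with "No tazemetostat dose re-escalation is permitted".

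**Interaction rule (Protocol 9.2.6 and Table 5).** If a moderate CYP3A inhibitor cannot be avoided, sites are to "reduce the dose of tazemetostat as shown in Table 5": 800 mg BID becomes 400 mg BID, 600 mg BID becomes "400 mg for first dose and 200 mg for second dose", and 400 mg BID becomes 200 mg BID. Three elimination half-lives after the inhibitor is discontinued, they are to "resume the tazemetostat dose that was being taken prior to initiating the inhibitor".

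Section 7.4.1, Table 1 and its footnotes do not mention CYP3A inhibitors or Table 5. Section 9.2.6 does not mention Table 1, toxicity reductions or the ban. The SAP does not address the point.

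**The concern.** Each rule works alone. The difficulty arises when a subject already on a Table 5 dose has a tazemetostat-related toxicity for which Table 1 lowers the dose level. The pre-inhibitor dose predates that toxicity, so resuming it cancels the reduction. A site that follows 9.2.6 literally then departs from 7.4.1, and a site that follows 7.4.1 departs from 9.2.6.

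The overlap is plausible on the protocol's own account. Section 9.2.5 warns that giving tazemetostat with a "strong or moderate CYP3A inhibitor increases tazemetostat plasma concentrations, which may increase the frequency or severity of adverse reactions". The moderate inhibitors listed in Table 4 include common drugs such as ciprofloxacin, fluconazole, diltiazem and verapamil.

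What is at stake is the dose an individual subject receives after a toxicity, and whether sites treat such subjects alike.

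**Working it through.** The plan gives no figure to reproduce. The check is a comparison of the two rules and a trace of the dose levels.

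**Inputs.** Table 1 levels: 800, then 600, then 400 mg BID, with no lower step. Table 5 conversions: 800 BID to 400 BID; 600 BID to 400 mg + 200 mg; 400 BID to 200 BID. Ban on re-escalation: 7.4.1. Resumption rule: 9.2.6.

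**Dose after the inhibitor has been stopped for 3 half-lives**

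| Sequence | Pre-inhibitor dose (what 9.2.6 resumes) | Table 1 level assigned during the course (ceiling under 7.4.1) | Nominal daily dose, 9.2.6 / Table 1 |
|---|---|---|---|
| A: one reduction during the course | 800 mg BID | 600 mg BID | 1600/1200 = 1.33 |
| B: already at 600 mg BID, next reduction during the course | 600 mg BID | 400 mg BID | 1200/800 = 1.50 |
| C: two reductions in one course | 800 mg BID | 400 mg BID | 1600/800 = 2.00 |
| D: already at 400 mg BID | 400 mg BID | no lower step (discontinue or discuss) | no conflict |

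Two further cases raise no conflict. If the toxicity reduction came before the inhibitor, the pre-inhibitor dose is already the reduced one. If there was no toxicity during the course, only the Table 5 step is being reversed.

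**Does anything else in the documents set the dose in A to C?**

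- Medical Monitor discussion is required for interruptions of more than 14 days, Grade 4 events and a fourth Grade 2 event. A first or second Grade 3 event that resolves within 14 days triggers none of these.
- Protocol 12.1.6 refers clinically significant laboratory abnormalities to 7.4.1. That governs the response to the abnormality. It does not say what dose follows when the inhibitor is withdrawn.
- Protocol 12.2.4.1.1 and 12.4 send Grade 3 or 4 neutropenia and thrombocytopenia through the SAE procedures, so the sponsor may learn of the event. That is reporting, not approval of the resumed dose.
- SAP Section 2 supersedes the protocol's statistical considerations only.

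None of these sets the dose after the inhibitor stops.

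**How often?** The documents give no rate for the overlap. Protocol 5.2.2 reports that the most common TEAEs leading to dose reduction each occurred in fewer than 1% of adults, and 9.2.6 lists moderate inhibitors among drugs to be used with caution. SAP 5.2 records that the trial stopped with 5 treated patients.

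**The case against.** The best defence is that the two sections serve different purposes and fit together when read that way. Section 9.2.6 sits under concomitant medication and reverses an interaction adjustment; 7.4.1 governs toxicity and is categorical. A careful investigator undoes the Table 5 step and keeps the Table 1 step. Section 12.1.6 leans the same way by pointing laboratory toxicities to 7.4.1. This largely stands: it is the sensible reading and the one most investigators would choose. It does not remove the point, because 9.2.6 names the dose to resume without qualification, and in this overlap that dose is the wrong one.

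Four stronger readings are tempting, and the documents do not support them.

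- *The rules clash in every inhibitor course.* The ban closes a paragraph about toxicity interruptions, so it is best read as leaving an ordinary return from Table 5 alone.
- *The instructions cannot be reconciled.* The reading by purpose reconciles them; the defect is that 9.2.6 does not state it.
- *While the inhibitor continues, Table 1 orders a restart above the dose at which toxicity occurred*, for example 600 mg BID after toxicity on 400 mg BID. Table 5 has rows for 600 and 400 mg BID, and 9.2.6 requires reduction through that table, so conversion is the natural reading. An increase at that point would also run against the ban in 7.4.1 itself.
- *The ratios in the table measure excess exposure.* They compare nominal doses. The toxicity arose on a reduced dose plus an inhibitor that raises plasma concentrations, and no exposure ratio was assumed.

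**Conclusion.** The point holds as a minor, patient-safety correction to a dosing rule. Where Table 1 reduces the dose level during a moderate CYP3A inhibitor course, 9.2.6 read literally restores the level that was removed: 800 against 600, 600 against 400, or 800 against 400 mg BID. That is contrary to 7.4.1.

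This rests on two assumptions: that Table 1 levels are counted from the pre-inhibitor dose, and that the toxicity falls within the inhibitor course.

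A reader might infer that the trial's results or error rates are touched. They are not: no endpoint, alpha, power or sample size figure depends on this, and under SAP Sections 8 and 9 no efficacy analysis is performed. With 5 treated patients, the practical consequence in this trial is small.

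**What to change.** Two sentences in an amendment.

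- In 9.2.6, replace the resumption instruction with: *Once the moderate CYP3A inhibitor has been stopped for 3 elimination half-lives, resume the lower of the pre-inhibitor dose and any Table 1 dose level assigned during the inhibitor course.*
- In 7.4.1, after the ban, add: *Return from a Table 5 adjustment alone is not re-escalation; Table 1 levels are set from the pre-inhibitor dose and converted through Table 5 while the inhibitor continues.*

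Applied to the sequences above, the first sentence gives min(800, 600) = 600 mg BID in A, min(600, 400) = 400 mg BID in B and min(800, 400) = 400 mg BID in C. With no toxicity it gives the pre-inhibitor dose. The second sentence is needed because moving from 400 mg + 200 mg to 600 mg BID after the inhibitor (600 to 1200 mg a day) is literally an increase that the ban would otherwise catch.

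A further cap at the dose on which the toxicity occurred should not be added. If toxicity arose on 400 mg BID with the inhibitor, and the inhibitor was stopped during the interruption, the new rule gives 600 mg BID while the cap could be read as 400 mg BID.

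The cost is two sentences, with no extra visits, subjects or analyses.

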9.2.7. Prohibitions and Restrictions During Study Period

Grapefruit, grapefruit juice-containing products, and Seville oranges are not permitted 1 week prior to the first dose of study drug and for the duration the study.

Phototoxic Potential: There are nonclinical data supporting a potential for phototoxicity, which has not been evaluated in humans. Hence, prolonged exposure to sunlight should be avoided during treatment. In addition, subjects should take other measures to avoid ultraviolet exposure such as wearing sunscreen and sunglasses, wearing protective clothing, and avoiding tanning beds. Refer to the tazemetostat IB for details.

9.3. Contraception and Pregnancy

There has been no experience to date of the use of tazemetostat during pregnancy or lactation. In an ongoing embryofetal development study, evidence of increased skeletal developmental abnormalities in fetuses from the pregnant rats relative to fetuses from control rats was observed. Consequently, there is a potential risk for teratogenicity, and precautions must be taken to avoid any pregnancy that could potentially be conceived during exposure to tazemetostat by either male or female subjects.

9.3.1. Definition of Childbearing Potential: Female Subjects

A female subject is considered of childbearing potential if she:

- Is anatomically and physiologically capable of becoming pregnant, and
- Will be or could possibly be sexually active with a male while undergoing study treatment

A female subject is considered to be of non-childbearing potential (i.e., physiologically incapable of becoming pregnant) if she:

- Is naturally postmenopausal (at least 12 months consecutively amenorrhoeic [amenorrhea following cancer therapy does not rule out childbearing potential] and without other known or suspected cause).
- Is surgically sterilized (i.e., total hysterectomy and/or bilateral oophorectomy) with surgery completed at least 1 month before the first dose of study drug.
- Has a documented congenital or acquired disorder that is incompatible with pregnancy.

9.3.2. Definition of Child-fathering Potential: Male Subjects

A male subject is considered of child-fathering potential if he:

• Is anatomically and physiologically capable of causing a pregnancy in a female partner,

and

• Will be or could possibly be sexually active with a female (who is or may become pregnant) while undergoing study treatment.

A male subject is considered to be of non-child-fathering potential if he:

Has a documented successful vasectomy (with medically confirmed azoospermia) or
male subjects must either practice complete abstinence or agree to use a latex or
synthetic condom during sexual contact with a pregnant female or FCBP from first
dose of study drug, during study treatment (including during dose interruptions), and
for 3 months after study drug discontinuation.

9.3.3. Pregnancy Prevention

9.3.3.1. Female Subjects

FCBP must either practice complete abstinence or agree to use a highly effective method of contraception beginning at least 28 days prior to the first dose of study drug, during study treatment (including during dose interruptions), for 6 months after tazemetostat discontinuation, and for 12 months after rituximab discontinuation. Female subjects must also not breastfeed or donate oocytes during study treatment and for 12 months following the last dose of rituximab. If the below contraception methods are not appropriate for the FCBP, she must be referred to a qualified contraception provider to determine the medically effective contraception method appropriate for the subject. The following are examples of highly effective methods of contraception (result in a failure rate of <1% per year when used consistently and correctly):

• Intrauterine device (IUD)

- Intrauterine hormone-releasing system (IUS)
- Hormonal (ovulation inhibitory combined [estrogen and progesterone]: oral, intravaginal, or transdermal; ovulation inhibitory progesterone-only: oral, injectable, or implantable)

NOTE: Due to the potential of enzyme induction with tazemetostat, hormonal contraception methods must be supplemented with a barrier method of contraception (preferably male condom)

- Bilateral tubal ligation
- Partner's vasectomy (if medically confirmed [azoospermia] and sole sexual partner)

NOTE: Female subjects of childbearing potential exempt from these contraception requirements are subjects who practice complete abstinence from heterosexual sexual contact. True abstinence is acceptable when this is in line with the preferred and usual lifestyle of the subject. Periodic abstinence (e.g., calendar, ovulation, symptothermal, or post ovulation methods) and withdrawal are not acceptable methods of contraception.

9.3.3.2. Male Subjects

Male subjects must have had a successful vasectomy (with medically confirmed azoospermia) OR must either practice complete abstinence or agree to use a latex or synthetic condom during sexual contact with a female of childbearing potential (FCBP) from first dose of study drug, during study treatment (including during dose interruptions), and for 3 months after study drug discontinuation.

NOTE: Male subjects must not donate sperm from first dose of study drug, during study treatment (including during dose interruptions), and for 3 months after study drug discontinuation

9.4. Treatment Compliance

Compliance for doses taken outside of the clinic may be assessed by a count of the tablets returned to the study trial site by the subject and review of doses taken with the subject. This will be recorded in the source documents, which may include the use of a subject medication diary per institutional practice.

9.5. Randomization and Blinding

This is a one-arm, open-label study, and therefore does not utilize randomization or blinding.

10. STUDY DRUG MATERIALS AND MANAGEMENT

10.1. Study Drug

Rituximab in combination with tazemetostat is under investigation as a treatment for subjects with R/R FL.

A description of the study drugs is provided in Table 6.

Table 6: Study Drugs

Product name	Study Drug (Tazemetostat)	Rituximab	Rituximab
Dosage form:	tablet	solution	solution
Unit dose:	200 mg	100 mg/10 mL or 500 mg/50 mL	1,400 mg/23,400 Units (1,400 mg rituximab and 23,400 Units hyaluronidase human) per 11.7 mL (120 mg/2,000 Units per mL)
Route of administration:	oral	intravenous	subcutaneous
Physical description:	red, round, and biconvex film-coated tablets packaged in white high-density polyethylene bottle with a child resistant, tamper-evident polypropylene screw cap	Refer to current manufacturer's prescribing information	Refer to current manufacturer's prescribing information
Manufacturer:	Manufactured for Epizyme by Patheon	Refer to current manufacturer's prescribing information	Refer to current manufacturer's prescribing information

Biosimilar formulations for rituximab will be allowed during the study.

10.2. Study Drug Packaging and Labeling

Tazemetostat will be supplied in white high-density polyethylene (HDPE) bottles, labeled in accordance with text that is in full regulatory compliance with each participating country and is translated into the required language(s) for each of those countries. Additional labeling can be added per institutional requirements. Additional labels must not obscure any information on the tazemetostat label.

Rituximab is available as single-dose vials of 100 mg/10 mL (10 mg/mL) and single-dose vials of 500 mg/50 mL (10 mg/mL) for IV, or single-dose vials of 1,400 mg rituximab and 23,400 Units hyaluronidase human per 11.7 mL (120 mg/2,000 Units per mL) for SC.

Protocol EZH-1401 Amendment 2.0 21 October 2021

The label(s) for IP will include Sponsor name, address, the protocol number, IP name, dosage form and strength (where applicable), amount of IP per container, lot number, expiry date (where applicable), medication identification/kit number, dosing instructions, storage conditions, and required caution statements and/or regulatory statements as applicable. Additional information may be included on the label as applicable per local regulations.

10.3. Study Drug Storage

Tazemetostat must be stored in a secure area, in compliance with the storage requirements listed on the label, with access limited to the Investigator and authorized site staff only. Tazemetostat tablets will be stored at temperatures below 25°C (77°F) in accordance with the labeled storage conditions. Refer to the pharmacy manual for details.

Rituximab will be refrigerated at 2°C to 8°C (36°F to 46°F). Rituximab vials should be protected from direct sunlight. Do not freeze or shake. Refer to the package label for further details and the current manufacturer's prescribing information.

10.4. Study Drug Preparation

No preparation is needed for tazemetostat.

For rituximab preparation, refer to the current manufacturer's prescribing information.

